#### **4.2 Non-investigational Product**

Other medications used as support or escape medication for preventative, diagnostic, or therapeutic reasons, as components of the standard of care for a given diagnosis, may be considered as non-investigational products.

In this protocol, non-investigational product(s) is/are the following:

- Dose Evaluation Phase (Stage 1): Not applicable
- Dose Expansion (Stage 2): For PAC subjects, if Stage 1 results in a decision to move to a randomized Phase 2 study with comparative arm in Dose Expansion Phase, Investigator's Choice for advanced or metastatic PAC subjects will be the comparator arm. The treatment options for 2L PAC include the following:
  - Gemcitabine with or without albumin-bound paclitaxel
  - Capecitabine and other fluoropyrimidine based regimens

#### **4.3 Storage and Dispensing**

The product storage manager should ensure that the study drug is stored in accordance with the environmental conditions (temperature, light, and humidity) as determined by BMS. If concerns regarding the quality or appearance of the study drug arise, the study drug should not be dispensed and contact BMS immediately.

Study drug not supplied by BMS will be stored in accordance with the package insert.

Investigational product documentation (whether supplied by BMS or not) must be maintained that includes all processes required to ensure drug is accurately administered. This includes documentation of drug storage, administration and, as applicable, storage temperatures, reconstitution, and use of required processes (eg, required diluents, administration sets).

Please refer to the current version of the Investigator Brochures and/or pharmacy manual or reference sheets for complete storage, handling, dispensing and infusion information for BMS-936564 (ulocuplumab) and BMS-936558 (nivolumab).

#### **4.3.1 Ulocuplumab (BMS-936564)**

Ulocuplumab (BMS-936564) vials must be stored refrigerated 2°C to 8°C in a tightly closed container and must be protected from light. If stored in a glass front refrigerator, vials should be stored in the carton. Once the ulocuplumab injection is transferred to the IV bag, it can be stored for a maximum of 12 hours at room temperature/under ambient light at 15°C - 25°C. If the solution in the IV bag cannot be used for infusion within the 12 hours at room temperature, it must be refrigerated at 2°C - 8°C, not to exceed 12 hours maximum in the refrigerator. The solution is stable for a total storage combination time of 24 hours.

Following transfer to the IV bag, preparation time of dilution to the end time of infusion should not exceed 24 hours as the diluted solution of BMS-936564 once prepared, must be infused within a 24 hour timeframe.

Any temperature deviations from the recommended storage conditions would require the site to contact the Sponsor for further instruction and disposition.

#### **4.3.2 Nivolumab (BMS-936558)**

Nivolumab (BMS-936558) vials must be stored at a temperature of 2°C to 8°C and should be protected from light, freezing and shaking. If stored in a glass front refrigerator, vials should be stored in the carton. Recommended safety measures for preparation and handling of nivolumab include laboratory coats and gloves.

#### Undiluted Nivolumab Injection and Diluted Nivolumab Injection in the IV Bag

The dosing calculations should be based on the body weight. Nivolumab injection is to be administered as an IV infusion over 60 minutes at 3 mg/kg.

The administration of nivolumab infusion must be completed within 24 hours of preparation. If not used immediately, the infusion solution may be stored under refrigeration conditions (2°C to 8°C) for up to 24 hours and a maximum of 4 hours of the total 24 hours can be at room temperature and room light. The maximum 4-hour period under room temperature and room light conditions includes the product administration period.

For details on prepared drug storage and use time of nivolumab under room temperature/light and refrigeration, please refer to the nivolumab Investigator Brochure sections 3.2.2 and 3.2.3 and/or pharmacy reference sheets.

#### **4.3.3 Ulocuplumab and Nivolumab Combination**

When both ulocuplumab and nivolumab are to be administered on the same day, separate infusion bags and filters must be used for each infusion. Ulocuplumab is to be administered first. The ulocuplumab infusion must be promptly followed by a saline flush to clear the line of ulocuplumab before starting the nivolumab infusion.

#### **4.4 Method of Assigning Subject Identification**

A subject number will be assigned through an interactive voice response system (IVRS) once the subject has signed the informed consent form and is registered. Specific instructions for using IVRS will be provided in a separate document.

Enrolled subjects that have met all eligibility criteria will continue with treatment assignment and drug vial assignment through the IVRS.

There will be two requirements for IVRS randomization in this study. The first one will occur in the Dose Evaluation Phase (Stage 1) after the DLT evaluation period. In this instance, the IVRS will be used to assign subjects to one of three cohorts for the dose evaluation (DL2, DL3A, DL3B). Additionally, if a randomized Phase 2 study with comparative arm is initiated in the Dose Expansion Phase (Stage 2), IVRS will be used to assign subjects to one of the two treatment arms.

#### **4.5 Selection and Timing of Dose for Each Subject**

Ulocuplumab will be administered every week or every two weeks depending on the cohort being evaluated. Nivolumab will be administered every two weeks for all cohorts. On the day of study drug administration, ulocuplumab is to be administered first. The second infusion will always be nivolumab, and will start no sooner than 30 minutes after completion of the ulocuplumab infusion.

For weekly ulocuplumab dosing, subjects may be dosed +/-1 day from their scheduled dosing date, but no less than 6 days between doses. For every 2 week dosing (ulocuplumab or nivolumab), subjects may be dosed  $\pm 2$  days from their scheduled dosing date, but no less than 12 days between doses. If dosing cannot be administered within the window of the scheduled dosing date, the dose will be considered a missed dose and the subject should come in for their next regular visit relative to Day 1. If the next regular visit is less than 6 days from the last ulocuplumab dose for weekly dosing, nivolumab may be administered alone for that visit.

Treatment compliance will be monitored by drug accountability as well as the subject's medical record and eCRF.

##### **4.5.1 Dose Delays and Interruptions**

###### **4.5.1.1 Ulocuplumab Dose Delay**

Investigators should, whenever possible, determine which medication is causing the toxicity and delay or dose reduce ulocuplumab and/or delay nivolumab, as applicable. If ulocuplumab is delayed due to an AE, nivolumab dosing may continue at the discretion of the Investigator. Ulocuplumab should be delayed for the following:

- Any Grade  $\geq 3$  drug-related AE, including laboratory abnormalities except for Grade 3 AEs that do not require nivolumab dose delay (see [section 4.5.1.2](#))

If the decision is to resume ulocuplumab dosing, the subject should restart treatment on the next regularly scheduled ulocuplumab dosing visit. Skipped doses are not to be replaced. If treatment is delayed > 6 weeks, the subject must be permanently discontinued from ulocuplumab therapy.

#### **4.5.1.2 Nivolumab Dose Delay**

Investigators should, whenever possible, determine which medication is causing the toxicity and delay or dose reduce ulocuplumab and/or delay nivolumab, as applicable. If nivolumab is delayed due to an AE, ulocuplumab dosing should also be delayed. Nivolumab should be delayed for the following:

- Any Grade  $\geq 2$  non-skin, drug-related AE, with the following exceptions:
  - Grade 2 drug-related fatigue or laboratory abnormalities do not require a treatment delay
- Any Grade 3 skin drug-related AE
- Any Grade  $\geq 3$  drug-related laboratory abnormality, with the following exceptions for thrombocytopenia, lymphocytopenia, AST, ALT, total bilirubin or asymptomatic amylase or lipase:
  - Grade 3 thrombocytopenia  $< 7$  days (not associated with Grade  $\geq 2$  hemorrhage) does not require dose delay
  - Grade 3 lymphocytopenia not associated with symptoms or clinical manifestations does not require dose delay. It is recommended to consult with the BMS Medical Monitor for Grade 3 lymphocytopenia.
  - Grade 3 drug-related amylase or lipase abnormality that is not associated with symptoms or clinical manifestations of pancreatitis does not require dose delay. It is recommended to consult with the BMS Medical Monitor for Grade 3 amylase or lipase abnormalities
  - If a subject has baseline AST, ALT, or total bilirubin that is within normal limits, delay dosing for drug-related Grade  $\geq 2$  toxicity
  - If a subject has baseline AST, ALT, or total bilirubin within the Grade 1 toxicity range, delay dosing for drug-related Grade  $\geq 3$  toxicity
  - If a subject has baseline AST or ALT within the Grade 2 toxicity range, delay dosing for drug-related elevations in AST and/or ALT  $> 2x$  baseline or a maximum of  $> 8x$  ULN
- Any adverse event, laboratory abnormality, or intercurrent illness which, in the judgment of the investigator, warrants delaying the dose of study medication

If the decision is to resume nivolumab dosing, the subject should restart treatment on the next regularly scheduled nivolumab dosing visit. Skipped doses are not to be replaced. If treatment is delayed  $> 6$  weeks, the subject must be permanently discontinued from all study therapy, except as specified in [Section 4.5.3.2](#).

Because of the potential for nivolumab-related AE requiring early recognition and prompt intervention, management algorithms have been developed and are included for suspected pulmonary toxicity, GI toxicity, hepatotoxicity, endocrinopathy, skin toxicity, neurological toxicity and nephrotoxicity. In order to standardize the management of AEs for all subjects, recommended treatment management algorithms are included in [Appendix 2](#). Adverse event treatment management algorithms included in the nivolumab IB might be considered for individual cases.

### **4.5.1.3 Criteria to Resume Nivolumab Treatment**

Subjects may resume treatment with nivolumab when the drug-related AE resolves to Grade  $\leq$  1 or baseline value, with the following exceptions:

- Subjects may resume treatment in the presence of Grade 2 fatigue
- Subjects who have not experienced a Grade 3 drug-related skin AE may resume treatment in the presence of a Grade 2 toxicity
- Subjects with baseline AST/ALT or total bilirubin in the Grade 1 or 2 toxicity range who require dose delays for reasons other than a 1 or 2-grade shift in AST/ALT or total bilirubin may resume treatment in the presence of Grade 2 AST/ALT OR total bilirubin
  - Subjects with combined Grade 2 AST/ALT AND total bilirubin values meeting discontinuation parameters ([Section 4.5.3.2](#)) should have treatment permanently discontinued
- Drug-related pulmonary toxicity, diarrhea, or colitis must have resolved to baseline before treatment is resumed
- Drug-related endocrinopathies adequately controlled with only physiologic hormone replacement may resume treatment

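### The second nivolumab restart exception in Protocol 4.5.1.3 omits the word *skin*, so read literally it permits redosing with an unresolved Grade 2 non-skin event that 4.5.1.2 says to hold for

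*Protocol*

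**What the plan says.** Protocol 4.5.1.2 sets the events for which nivolumab should be held. One trigger is any Grade 2 or higher "non-skin, drug-related AE, with the following exceptions", and the exception at Grade 2 is short: "Grade 2 drug-related fatigue or laboratory abnormalities do not require a treatment delay". For skin the trigger is higher: "Any Grade 3 skin drug-related AE". On restarting, it says: "If the decision is to resume nivolumab dosing, the subject should restart treatment on the next regularly scheduled nivolumab dosing visit". Skipped doses are not made up. A delay of more than 6 weeks ends all study treatment, subject to the exceptions in 4.5.3.2. Ulocuplumab is to be held whenever nivolumab is held for an adverse event.

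Protocol 4.5.1.3 sets the restart conditions. The general rule begins "Subjects may resume treatment with nivolumab when the drug-related AE resolves to Grade" and sets the level at 1 or lower, or the baseline value. Exceptions follow. The first is "Subjects may resume treatment in the presence of Grade 2 fatigue". The second is the bullet at issue: "Subjects who have not experienced a Grade 3 drug-related skin AE may resume treatment in the presence of a Grade 2 toxicity". Later bullets deal with liver tests, with controlled endocrinopathies and, more strictly than the general rule, with lung and bowel events: "Drug-related pulmonary toxicity, diarrhea, or colitis must have resolved to baseline before treatment is resumed".

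**The concern.** The two halves of the second bullet do not match. The condition is the absence of a Grade 3 drug-related skin event. The permission is to restart with a Grade 2 toxicity of unstated type. The fatigue, liver-test, lung and bowel, and endocrine bullets all name the toxicity they cover; this one does not.

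Most subjects will presumably never have a Grade 3 skin event. For them the literal bullet replaces the Grade 1 restart standard at Grade 2 for every event without a rule of its own. Sites would then have two instructions for the same event, hold under 4.5.1.2 and may resume under 4.5.1.3, and could manage like subjects differently. At stake are redosing into an unresolved event, who reaches the 6-week stopping rule and, for an event early in treatment, possibly whether a delay counts as a dose-limiting toxicity.

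**Working it through.** The plan states no figure on this point, so the check is a comparison of texts followed by the dosing calendar.

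**Step 1. One subject under both sections.** Take a subject with no Grade 3 skin event and a new drug-related joint event that stays at Grade 2. Joint events have no bullet in 4.5.1.3. They are also not among the seven toxicity types that 4.5.1.2 lists as having an Appendix 2 algorithm (lung, gastrointestinal, liver, endocrine, skin, neurological, renal).

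| Rule | Instruction while the event is Grade 2 |
|---|---|
| 4.5.1.2, non-skin trigger | Hold |
| 4.5.1.3, general rule | Wait for Grade 1 or lower, or baseline |
| 4.5.1.3, second bullet as printed | May restart |
| 4.5.1.3, second bullet with *skin* added | Does not apply, so wait |

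The printed bullet is the only line that permits restart.

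**Step 2. Which reading fits the rest.** If the bullet covered any Grade 2 toxicity, the separate fatigue bullet would be unnecessary for everyone without a Grade 3 skin event. If it covers skin only, the sections agree: skin events trigger a hold only at Grade 3, so allowing restart at Grade 2 skin toxicity is the natural counterpart.

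**Step 3. Where the literal permission stops.** Lung toxicity, diarrhea, colitis, liver tests, controlled endocrinopathies, infusion reactions and certain Grade 2 eye events have their own rules in 4.5.1.3, 4.5.3.2 or 4.5.4. Other Grade 2 laboratory abnormalities do not require a hold. The affected group is the remaining Grade 2 non-skin events.

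**Step 4. Timing.** Inputs are nivolumab every 14 days, restart only at a scheduled nivolumab visit, and a limit of 6 × 7 = 42 days. The delay at successive visits after a held dose is:

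- 1 × 14 = 14 days
- 2 × 14 = 28 days
- 3 × 14 = 42 days, which equals the limit but does not exceed it
- 4 × 14 = 56 days, which exceeds it

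For an event that stays at Grade 2, the printed bullet allows restart at 14 days. The general rule allows none at 14, 28 or 42 days. A subject still at Grade 2 on day 42 therefore passes the limit and stops unless 4.5.3.2 exempts the delay.

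**Step 5. Dose-limiting toxicity, as an illustration only.** Suppose both drugs are held from Day 15 on the weekly ulocuplumab schedule, with the last ulocuplumab dose on Day 8.

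- *Printed bullet:* restart on Day 29. By the delay formula in SAP 7.4.2.2, the ulocuplumab delay is (29 − 8) − 7 = 14 days. That is not more than 14, so it is not a dose-limiting toxicity on this criterion. Two of six doses are missed, leaving 4, below the 5 that 3.1.4 requires for evaluability.
- *General rule:* the event is still Grade 2 on Day 29, so the hold continues past 14 days and counts as a dose-limiting toxicity under 3.1.4.

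**The case against.** The best reply is that context settles the meaning. The condition is about skin, 4.5.1.2 treats skin and non-skin events differently, and the broad reading would swallow a neighboring bullet. A careful site would supply the missing word. The bullet is also only permissive, investigators may hold for any event in their judgment, and the hold rule in 4.5.1.2 arguably applies afresh at each visit while the event remains at Grade 2. Departing from the Grade 1 standard is in itself what an exception does.

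Much of this stands, and it limits the exposure. It does not remove the conflict. The protocol does not say which section prevails when the hold list and the restart list disagree, and a redosing rule should not depend on readers supplying a word. Section 4.5.1.2 itself gives standardized management of events as the reason for including the algorithms.

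Three further limits are fair:

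- The stopping-rule difference narrows where a prolonged steroid taper or another 4.5.3.2 exception covers the delay.
- The Appendix 2 figures cannot be read in the public text and may settle neurological or renal events, so the case here rests on joint events. The nivolumab brochure algorithms, which 4.5.1.2 allows for individual cases, could not be consulted.
- The dose-limiting toxicity consequence needs several things to coincide, and the documents give no rate for it.

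**Conclusion.** The concern holds. As printed, the second restart exception permits redosing with an unresolved Grade 2 non-skin drug-related event for which 4.5.1.2 says nivolumab should be held, and nothing readable in the protocol or SAP confines it to skin. For a persistent Grade 2 event, the two readings separate at the first visit after the held dose (14 days) and end in different outcomes once the delay exceeds 42 days. How many subjects this would affect cannot be estimated from the documents.

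That *skin* was the intended word is a strong inference, but the documents do not state it. This is a wording error in an operative safety rule. It should be corrected, but it challenges no design decision and changes no sample size, power or error rate.

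**What to change.** Insert *skin* so that the permission at the end of the second bullet in 4.5.1.3 reads: a Grade 2 skin toxicity. The condition at the start of the bullet stays as it is. This restores agreement with 4.5.1.2 and leaves the other exceptions untouched. It is a one-word change that can go out by clarification letter or in the next amendment, and it needs no additional patients, visits or procedures.

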### **4.5.1.4 Ulocuplumab or Nivolumab Dose Interruptions**

If an ulocuplumab infusion is interrupted or an ulocuplumab-related infusion reaction prevents subsequent infusion of nivolumab on the same day, the dose of nivolumab should be replaced as soon as possible. In such instances, at least 12 days must elapse between the replacement dose of nivolumab and the administration of the next dose of ulocuplumab combined with nivolumab to maintain a 2 week period (+/-2 days) in between nivolumab dosing.

## **4.5.2 Dose Modifications**

### **4.5.2.1 Ulocuplumab Dose Modification Criteria**

Investigators should, whenever possible, determine which medication is causing the toxicity and delay or dose reduce ulocuplumab and/or delay nivolumab, as applicable. Depending on the nature of the AE, inpatient ulocuplumab dose modifications may occur according to [Table 4.5.2.1-1](#). The following rules apply when modifying the dose of ulocuplumab:

- Assessment of causality must be determined and documented by the Investigator and also discussed by the BMS Medical Monitor
- Following implementation of a dose reduction for ulocuplumab, the dose should not be re-escalated
- If the same AE recurs despite a dose reduction, a second dose reduction versus discontinuation of the subject from ulocuplumab will be discussed and agreed upon by the Investigator and BMS Medical Monitor

**Table 4.5.2.1-1: Ulocuplumab Dose Modification Criteria**

Adverse Event	Dose Delay (refer to section 4.5.1.1)	Criteria to Resume Ulocuplumab Treatment			
		For DL-1	For DL1	For DL2	For DL3A/3B
Any Gr ≥ 3 drug-related AE, including laboratory abnormalities, except for Grade 3 hematologic AEs listed below or other exceptions listed in section 4.5.1	Hold ulocuplumab until return to baseline or Grade ≤ 1, whichever is lower	1st event: Discontinue ulocuplumab	1st event: Resume at 200 mg weekly	1st event: Resume at 400 mg weekly	1st event: Resume at 800 mg weekly
			2nd event: Discontinue ulocuplumab	2nd event: Resume at 200 mg weekly	2nd event: Resume at 400 mg weekly
				3rd event: Discontinue ulocuplumab	3rd event: Discontinue ulocuplumab
Any Gr3 drug-related neutropenia, Gr3 thrombocytopenia > 7 days	Hold ulocuplumab until return to baseline or Grade ≤ 1, whichever is lower	2nd event: Discontinue ulocuplumab	1st event: Resume at 200 mg weekly	1st event: Resume at 400 mg weekly	1st event: Resume at 800 mg weekly
			3rd event: Discontinue ulocuplumab	2nd event: Resume at 200 mg weekly	2nd event: Resume at 400 mg weekly
				3rd event: Discontinue ulocuplumab	3rd event: Discontinue ulocuplumab
Gr4 asymptomatic lipase or amylase elevations	Hold ulocuplumab until return to baseline or Grade ≤ 1, whichever is lower	All events: Resume at same dose. Consult with BMS Medical Monitor if recurrent or sustained.			

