**4.5.3 Discontinuation Criteria**

**4.5.3.1 Ulocuplumab Discontinuation Criteria**

Discontinuation criteria apply for all drug-related AE attributed to ulocuplumab and consist of the following:

- Grade ≥ 3 thrombocytopenia associated with bleeding (occurring concomitant with ≥ Grade 2 hemorrhage)

- Grade  $\geq 3$  drug-related infusion reaction of any duration
- Any Grade 4 drug-related AE or laboratory abnormality except for Grade 4 AE listed as exceptions to the nivolumab discontinuation criteria (see section 4.5.3.2)
- Any recurring drug-related Grade  $\geq 3$  AE or laboratory abnormality that requires multiple dose reductions of ulocuplumab (see specific criteria in [section 4.5.2.1](#))
- Any drug-related AE resulting in dose delay of ulocuplumab  $> 6$  weeks
- Any AE, laboratory abnormality, or intercurrent illness which, in the judgment of the Investigator, presents a substantial clinical risk to the subject with continued ulocuplumab dosing

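### Table 4.5.2.1-1 tells sites at DL1 and above to resume ulocuplumab after some events for which Sections 4.5.3.1 and 4.5.4 require a permanent stop, and does not refer to either section.

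*Protocol*

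**What the plan says.** Protocol Section 4.5.2.1 introduces Table 4.5.2.1-1 in permissive terms, asks for causality to be documented and discussed with the Medical Monitor, and leaves the rest to the table. The two rows that matter here are:

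- Row 1: "Any Gr ≥ 3 drug-related AE, including laboratory abnormalities, except for Grade 3 hematologic AEs listed below", together with a reference to the exceptions in Section 4.5.1. After recovery, the first event leads to a restart at 200 mg (DL1), 400 mg (DL2) or 800 mg (DL3A/3B) weekly. At DL-1 the first event ends ulocuplumab.
- Row 2: "Any Gr3 drug-related neutropenia, Gr3 thrombocytopenia > 7 days". At DL1 and above the first event again leads to a restart one step down.

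Section 4.5.3.1 lists six reasons to discontinue ulocuplumab, for drug-related events attributed to it. The first is "Grade ≥ 3 thrombocytopenia associated with bleeding", defined by concurrent hemorrhage of Grade 2 or more. The second is a Grade 3 or higher "drug-related infusion reaction of any duration". The third is "Any Grade 4 drug-related AE or laboratory abnormality except for Grade 4 AE listed as exceptions to the nivolumab discontinuation criteria". Section 4.5.4 separately orders permanent discontinuation after a Grade 3 or 4 infusion reaction. Section 3.5 lists the criteria in 4.5.3.1 and 4.5.3.2 among the reasons for which stopping is mandatory.

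**The concern.** The table is what a site consults when deciding whether and at what dose to restart ulocuplumab. For a severe infusion reaction, a non-exempt Grade 4 event or bleeding thrombocytopenia, it gives a restart dose at DL1 and above, while another section says the drug is finished for that subject. A site using the table alone could re-dose a subject whom the protocol elsewhere says must not be re-dosed. What is at stake is subject safety and uniform conduct across sites.

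The escalation decision is little affected. Under Section 3.1.4, a ulocuplumab dose reduction for a drug-related event in the DLT period counts as a DLT, and so does a toxicity managed by stopping the drug. Either action is counted.

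**Working it through.** No arithmetic beyond counting applies, so I set each stop criterion in Section 4.5.3.1 against the rows of the table.

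| 4.5.3.1 criterion | Where the event falls in the table | Table action at DL1 and above | Conflict? |
|---|---|---|---|
| 1. Grade ≥ 3 thrombocytopenia with Grade ≥ 2 hemorrhage | Grade 3 beyond 7 days: row 2. Grade 4, or Grade 3 of 7 days or less: row 1 | Resume at lower dose | Yes |
| 2. Grade ≥ 3 infusion reaction (also 4.5.4) | Row 1 | Resume at lower dose | Yes |
| 3. Non-exempt Grade 4 event | Row 1 | Resume at lower dose | Yes |
| 4. Recurrence needing multiple reductions | Refers back to 4.5.2.1 | As counted in the table | No |
| 5. Delay over 6 weeks | Delay column refers to 4.5.1.1, which carries the stop | Stop | No |
| 6. Investigator judges substantial risk | Judgement, not a table entry | None | No |

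Three of six criteria therefore meet an instruction to resume.

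**Do row 1's own exclusions remove these events?** Row 1 leaves out the Grade 3 hematologic events in row 2 and the exceptions in Section 4.5.1.

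- The exception in 4.5.1.1 is for Grade 3 events that need no nivolumab delay, so it cannot reach Grade 4.
- A Grade 3 infusion reaction is a non-skin drug-related event above Grade 2. It does require a nivolumab delay under 4.5.1.2, so it stays in row 1.
- Short Grade 3 thrombocytopenia (under 7 days) is excepted in 4.5.1.2 only without Grade 2 or higher hemorrhage, so the bleeding case also stays in row 1. Row 2 has no such qualifier.

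Row 3, "Gr4 asymptomatic lipase or amylase elevations", resumes at the same dose. It agrees with the stop rules, because 4.5.3.2 lists that event as an exception.

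**How many instructions?** Lower-dose resume entries, as they appear in the extracted table, are:

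- Row 1: 1 (DL1) + 2 (DL2) + 2 (DL3A/3B) = 5.
- Row 2: 1 + 2 + 2 = 5.
- Total 10, of which 1 + 1 = 2 are in the DL1 column.

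**Who can still be affected?** SAP Section 2 reports more than 2 DLTs at DL1, the opening of DL-1, and no ulocuplumab dose reductions at DL1. Protocol Section 3.1.1 then completes Stage 1 at DL-1 if it is tolerable, with no stated route back to DL2 or DL3. That leaves the 2 DL1 entries. The Rolling Six limit in 3.1.1 caps DL1 at 6 subjects, tumor types combined. At DL-1, row 1 discontinues at the first event, in line with the stop rules.

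**Is precedence stated?** Neither the table nor the text of 4.5.2.1 mentions 4.5.3.1 or 4.5.4. The only text that settles the order is Section 3.5.

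**The case against.** The best reply is that the protocol, read as a whole, already answers the question. Section 3.5 makes the stop criteria mandatory, 4.5.3.1 and 4.5.4 state them independently, and 4.5.2.1 only permits modifications according to the nature of the event. A mandatory stop outranks a permissive table. This stands as far as it goes: it shows which rule should win, and that the policy is not undecided. It does not mend the table, which still gives the opposite instruction where the dosing decision is made. The Medical Monitor discussion required in 4.5.2.1 is about causality, not about whether a stop criterion is met.

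Two limits on scope also stand. Section 4.5.3.1 covers only events attributed to ulocuplumab, whereas the table speaks of drug-related events generally. And very few subjects can still meet the conflict.

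A reader might infer more than the documents support:

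- *That the open DL-1 cohort is exposed through row 2.* The visible DL-1 entry is "2nd event: Discontinue ulocuplumab", which could suggest that a first bleeding event is not a stop. No first-event entry is visible, and the DL1 cell beside it skips from a first to a third event. Text may have been lost in extraction, so nothing should rest on that cell.
- *That row 1 at DL-1 contradicts the Grade 4 exemptions carried over from 4.5.3.2.* It is a stricter rule at the lowest dose, not an opposite one. Whether to relax it is a clinical choice.
- *That the 6-week limit in 4.5.1.1 conflicts with the steroid-taper allowance in 4.5.3.2.* The two can be read together: ulocuplumab stops while nivolumab resumes. SAP Section 7.4.2.3 provides for nivolumab continuing alone.

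**Conclusion.** The point holds for DL1 and above. For ulocuplumab-attributed events, rows 1 and 2 instruct a restart at a lower dose after three kinds of event for which 4.5.3.1 requires discontinuation. For one of them, severe infusion reactions, 4.5.4 requires it too. Section 3.5 shows that the stop should prevail, so this is a wrong instruction in a table rather than a gap in policy.

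The practical size is small: at most 6 DL1 subjects, fewer if some are already off treatment, with no dose reduction reported there. The documents give no basis for estimating how many would have such an event. The conclusion assumes that the row 1 text and the DL1-and-above first-event entries were extracted correctly, and that DL2 and DL3 are not reopened. If they were, the other 8 resume entries would become live. It is still worth correcting, because the rule concerns safety and the change is slight.

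**What to change.** At the next amendment, add to the event description in rows 1 and 2: 'not meeting the discontinuation criteria in 4.5.3.1 or 4.5.4'. Add a footnote to the table: 'Sections 4.5.3.1 and 4.5.4 take precedence over this table; recurring events are counted as shown in the table.'

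The second clause of the footnote is needed because the fourth criterion in 4.5.3.1, on recurring events "that requires multiple dose reductions of ulocuplumab", refers back to 4.5.2.1. A bare precedence rule could be read as cancelling the second-event reductions that the table intends at DL2 and DL3A/3B.

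The cost is two row labels, one footnote and a short memo to sites. No subjects, procedures or analyses are added, and the DLT definition in 3.1.4 is unchanged.
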